7.2 RATIONALE

In the RMP approved by the EMA's PRAC, dated 23 September 2015, a PASS was implemented as part of pharmacovigilance plan of the RMP for Praluent, in response to PRAC request.

At that time, only 2 dosage regimens, 75 mg once every two weeks and 150 mg once every two weeks, were approved in European Union; therefore, this drug utilization study was designed to assess, in Europe, the effectiveness of the dosing recommendation included in the labeling for these 2 approved dosage regimens to avoid very low LDL-C levels; however, a new dosage regimen of 300 mg once every 4 weeks (monthly) was approved in European Union and the updated SmPC was approved on 14 November 2016 (6). Consequently, the study design was updated to reflect the administration of the new approved dosage regimen in a real world setting.

8 RESEARCH QUESTION AND OBJECTIVES

8.1 PRIMARY OBJECTIVE

The primary objective of this study is to assess the effectiveness of the Praluent (brand name of alirocumab) dosing recommendations for the 3 dosage regimens approved to date, ie, 75 mg once every two weeks, 150 mg once every two weeks, and 300 mg once every 4 weeks (monthly) to avoid very low LDL-C levels.

8.2 SECONDARY OBJECTIVES

The secondary objective of this study is to describe the pattern of Praluent utilization in real-world clinical practice with respect to the dosing recommendations in the labelling of the 3 dosage regimens approved to date, ie, 75 mg once every two weeks, 150 mg once every two weeks, and 300 mg once every 4 weeks (monthly) to avoid very low LDL-C levels.

9 RESEARCH METHODS

9.1 STUDY DESIGN

This study is a non-interventional (with regard to the therapeutic strategy), retrospective cohort study in patients who were initiated with Praluent (brand name of alirocumab), 75 mg once every two weeks, 150 mg once every two weeks, or 300 mg once every 4 weeks (monthly).

The clinical setting and data sources of the study will mirror real life management of those patients.

9.2 SETTING

This study is planned to be conducted in European countries and consists of 3 waves. Germany, United Kingdom, Belgium, and Netherlands participated in Wave 1; for Wave 2 and Wave 3, the following countries have been selected based on the extent of patient exposure estimated from EU sales data: Austria, Belgium, Germany, Italy, Netherlands, Spain, and United Kingdom in Wave 2; Austria, Belgium, Italy, Netherlands, Spain, and United Kingdom in Wave 3. The availability of essential data, in particular the LDL-C values that will allow the MAH to assess the objectives of the study, will be ensured during the physician selection. According to the feasibility assessment result, the vast majority of the responding sites in the selected countries collect LDL-C values.

9.2.1 Duration of the study

The study will be conducted in 3 waves during 3 consecutive years.

The rationale for conducting the 3 waves when treatment patterns are evaluated across 3 different cohorts of Praluent prescribers and their patients is as follows:

- To confirm the effectiveness of the SmPC dosing recommendations risk minimization measures observed in the repeated waves.
- To observe the trend in practice over time, if any, by comparing findings across the 3 waves.
- Using 3 waves will also allow getting preliminary data available sooner, with the earliest availability at the end of the first wave.

After the first Praluent prescription identified during the eligibility period (Mar to Jun 2017 for Wave 1, Jul 2017 to Jun 2018 for Wave 2, and Jul 2018 to Jun 2019 for Wave 3), the observation period will last 6 months for each patient: from their first prescription to 6 months later, at the latest until the end of December 2017, 2018 and 2019, respectively.

After the end of the 6-month observation period, submission of appropriate documentation to Regulatory Authorities (if applicable according to local regulations) and/or Ethics Committees will be performed, in parallel, the physicians will be enrolled and informed of the main purpose of the study and upon all relevant approvals are obtained, the patients will be selected up to the first quarter (Q1) of 2019, 2020, and 2021 following the observation period, respectively.

The data will be collected retrospectively from the second quarter (Q2) 2018 to Q1 2019 in Wave 1, from Q1 2019 to Q1 2020 in Wave 2 and from Q1 2020 to Q1 2021 in Wave 3, respectively. Please see details in Figure 1 and Figure 2.

Figure 1 - Annual study progress in Wave 1

Wave 1

[figure not shown]
[figure not shown]

Figure 2 - Annual study progress in Waves 2 and 3

Waves 2 and 3

9.2.2 Eligibility criteria

9.2.2.1 Inclusion criteria

Physicians who meet the following inclusion criterion will be eligible to participate in this study:

I 01. At least one initial prescription of Praluent during the eligibility period.

Eligible patients for retrospective data collection will be those meeting the following criteria:

- I 02. Initiated with Praluent following a first prescription during the eligibility period.
- I 03. Signed written informed consent, if it is required by the country.

9.2.2.2 Exclusion criteria

Physicians who meet one or more of the following exclusion criteria will be excluded from this study:

- E 01. Have participated in any randomized clinical trials with Praluent (alirocumab).
- E 02. Have participated in a previous wave of this study.

Patients who meet one or more of the following exclusion criteria will be excluded from this study:

- E 03. Have participated in any randomized clinical trials with Praluent (alirocumab).
- E 04. Medical chart not retrievable, empty or missing.

9.2.3 Analysis populations

The analysis population will consist of all patients included in the study and meeting all inclusion criteria. This population will be the eligible population.

Physicians who included at least one patient in the patient analysis population will be part of the physicians' analysis population.

9.2.4 Modalities of recruitment

9.2.4.1 Physician selection

National prescriber databases containing health care professionals' information and their prescribing information, will be used to identify sites in each selected country.

For each wave, a 3-step process will be followed: identification from prescription database(s), selection, and remote recruitment.

• Identification: sites' prescribing volume of Praluent will be identified via Xponent database (or equivalent databases of prescriptions received in pharmacies). Additional databases will be selected in each country of interest to better identify the prescribers. Then, physicians/practices/institutions (depending on each country's data privacy limitations) with Praluent prescription during the eligibility period will be identified via OneKey database (or similar databases of physicians and/or hospital information). The prescribing physicians will be specialists (mainly, but not limited to, cardiologists, endocrinologists and internists) and/or general practitioners.

The clusters and physicians that have the highest likelihood of having prescribed Praluent and of participating in the study will be contacted regardless of their level of prescription. Representativeness of study sample with respect to the prescription level will be assessed a posteriori in the analysis phase (details in Section 9.7.3).

- **Selection:** the selection of physicians/practices/institutions will be performed based on availability of eligible patients. The selection process will be summarized by country in the study reports.
 - A physician can only participate in 1 wave of this study, and no more than 2 physicians from the same practice/institution can participate in each wave of this study.
 - Physicians who have participated in any randomized clinical trials with Praluent (alirocumab) will be excluded from this study.
- **Recruitment**: physicians will then be recruited remotely (over the phone or by e-mail) after the end of the 6-month observational period:
 - The physician will be informed on the main purpose of the study, ie, assessing the effectiveness of the SmPC dosing recommendation to avoid very low LDL-C, collecting key characteristics and treatment approaches for Praluent-treated patients in a real world setting, and on the general design of the study (CRF, electronic platform). The physician will be informed that there is no need to interview his/her patients in order to conduct the study, except to get their consent in order to collect their data retrospectively, when informed consent is required by local regulation. Data availability from the 6-month observation period, and particularly critical variables such as LDL-C values, will be secured at the time of site selection through a questionnaire.
- A total of 20 physicians in Wave 1 and 61 physicians in Wave 2 were enrolled across all
 the participating countries. About 36 to 63 physicians are expected to be enrolled in
 Wave 3.

The detailed physician selection process will be described in a separate study plan which will be generated at study launch and updated during the conduct of the study, describing each wave separately.

It is likely that physicians who participate in this study may be different from those who do not with respect to specialty. It is anticipated that specialists are more likely to participate. The specialty, level of prescriptions, and reason for refusal (if available) will be described for the physicians who do not accept participation in the study.

9.2.4.2 Patient selection

Following site activation and staff training, the site staff will compile a patient roster from their prescription records according to the eligibility period.

For sites with more than 8 potential eligible patients, sites are asked to list their potential patients and assign them each a consecutive number. The CRO will use a random selection tool that randomly orders the previously consecutive numbers and instructs the sites which numbers were ranked as top 8. The site will look back at their list of patients and will enroll the patients with the assigned numbers that were ranked as the top 8. Should any of these 8 patients not be eligible for enrollment, the patient assigned to the next number (ie, ranked 9th) from the randomization tool will be approached.

When required by local regulation, site staff will contact patients for consent. The site might be facing the following scenarios:

- Remote consent for the patients who are not scheduled to return to the office within 1 month time. The site will contact the patient by phone to explain the study and will send the Informed Consent Form (ICF) to the patients who have interest to return, signed and dated. Patients will have the opportunity to ask questions over the phone and they will be able to decide freely if they wish to participate.
- Face to face consent for patients who will return to the office within 1 month. The ICF will be signed and dated during this visit.

Site staff will keep a patient log to track anonymous information on the patients who refuse to participate (please see Section 9.6.4).

For each participating physician, up to 8 patients will be randomly enrolled. If the number of patients treated by physician is less than 8, no random selection will be needed. If there are 2 physicians from the same practice/institution participating in the same wave of the study, the combined total number of patients selected from these 2 physicians will be limited to 10 and a random selection of 10 patients will be performed.

Patients who have participated in any randomized clinical trials of Praluent (alirocumab) will be excluded from this study.

9.3 VARIABLES

Physicians' characteristics will be collected at the time of physician recruitment.

All patient variables from the index date (the date of the first prescription of Praluent) to the end of the observational period will be retrospectively collected:

- Patient characteristics (please refer to Section 9.3.2).
- Prescriptions of Praluent and other lipid-lowering drugs in the observational period.

- LDL-C value prior to or on the index date and all LDL-C values during the observation period.
- Any adverse event identified in the patient record during the retrospective chart review (please refer to Section 11).

9.3.1 Physician characteristics

Physician level of Praluent prescription, specialty and/or setting type, and localities will be collected. The physician will also be asked if he is/was involved in another observational study of Praluent.

9.3.2 Patient characteristics

- 1. Demographics: age, sex.
- 2. Height, weight, and body mass index (where available).
- 3. Smoking status (ie, Never Smoker, Former Smoker, or Current Smoker).
- 4. Medical history: at baseline (prior to or on the index date):
 - (1) Diagnosis of hypercholesterolemia,
 - (2) Type of familial hypercholesterolemia,
 - (3) Clinical atherosclerotic cardiovascular disease (ASCVD) that includes acute coronary syndromes, or history of myocardial infarction, stable or unstable angina, coronary or other arterial revascularization, ischemic stroke, transient ischemic attack, or peripheral arterial disease presumed to be of atherosclerotic origin,
 - (4) Hypertension,
 - (5) Diabetes,
 - (6) Congestive heart failure,
 - (7) Arrhythmia,
 - (8) Chronic kidney disease (Stage 3 or 4).

9.3.3 Prescriptions of Praluent

- 1. Date of initial prescription,
- 2. Dose and dosing frequency,
- 3. Number of doses prescribed,
- 4. Number of renewals, date(s) of renewal(s), and dosage and dosing frequency at renewals,
- 5. Reason for any Praluent dosage regimen modification.

9.3.4 Discontinuation of Praluent, if relevant

- 1. Date of discontinuation;
- 2. Reason for discontinuation:
 - (1) Description of reason, if available.
 - (2) Unspecified.

9.3.5 Prescription of other lipid lowering drugs

Prescription of other PCSK-9 inhibitors, statins, ezetimibe, bile acid-binding resins, nicotinic acid and fibrates, at the time of the index prescription of Praluent and any prescriptions during the observational period:

- 1. Generic name of drug (international nonproprietary name [INN]);
- 2. Date of prescription;
- 3. Dose;
- 4. Dosing frequency.

9.3.6 LDL-C values

The most recent value prior to or on the index date (baseline) and all values in the observational period:

- 1. Date of the test.
- 2. Value of LDL-C.

9.3.7 Adverse events

An adverse event (AE) is any untoward medical occurrence in a patient or in a clinical investigation subject administered a pharmaceutical product, and which does not necessarily have a causal relationship with that treatment. An adverse event can thus be any abnormal laboratory finding, symptom or disease temporally associated with the use of a medicinal (investigational) product, whether or not caused by that product.

Adverse events will be collected from the initiation of Praluent until the end of the 6-month observational period with the following details:

- 1. Nature of AE, such as hospitalization, onset of new disease, a new symptom, worsening of an existing condition, or lab abnormalities...
- 2. Start date/end date and outcome
- 3. Action taken with Praluent, if any: discontinuation, delay, or dose change.

9.3.8 Date on which the patient is no longer managed by the treating physician

Date on which the patient is no longer managed by the treating physician will be collected, if it is applicable.

9.4 DATA SOURCES

As soon as the ICF is signed and dated by the patient, the data abstraction can be started. Hence, data from medical records (either EMRs or paper source files) for each participating patient will be extracted and completed by site personnel and/or trained and authorized external abstractors using an e-CRF.

For patients in whom Praluent will be initiated by a given physician, and who will then be followed by another physician, all efforts will be made to collect data from these multiple caregivers.

9.5 STUDY SIZE

9.5.1 Determination of sample size

According to the global pool of Phase 2 and Phase 3 studies, 42.7% of patients treated with Praluent (alirocumab) had at least 1 value of LDL-C <25 mg/dL¹, regardless of the dose of Praluent received and the baseline LDL-C level. Compared to what is expected in the real clinical practice, this percentage is probably overestimated as the very low LDL-C levels occurred mostly during the Long Term study in which patients were initiated and maintained at 150 mg throughout the study, independent of the LDL-C baseline, to evaluate the long term safety of Praluent administered at the highest dose. In Wave 1 of the study, a total of 61 patients had at least one LDL-C value available during the 6-month observation period (irrespective of baseline LDL-C data availability); among those, three patients (4.9%) had an LDL-C level of <25mg/dL.

The following table shows the exact 95% confidence intervals for a range of possible proportions of patients with very low LDL-C value for different study sizes (<25 mg/dL or <0.65 mmol/L). For the global analysis gathering the 3 waves with total number of patients ranging from approximately 454-574 and assuming approximately 5% of the patients will have an LDL-C level of <25 mg/dl based on the observed data for Wave 1, the half-width will range from 1.85% (95% CI = 3.4, 7.1) to 2.1% (95%CI=3.2, 7.4) for the observed proportion of 5% (Table 3), which is deemed sufficient.

¹ In the clinical trials, only patients who achieve 2 consecutive calculated LDL-C <25 mg/dL were monitored according to a specific process and only these figures were presented in each CSR and submitted files.

09-Jul-2020 Version number: 1

Table 3 - Exact 95% confidence intervals for different study sizes and possible proportions of patients with very low LDL-C level (%)

% patients with very low LDL-C	Number of Patients						
	68	135	251	255	454	574	875 (total number planned in 2018)
1	0 , 7.1	0.1 , 4.5	0.2 , 3.2	0.2 , 3.1	0.3 , 2.4	0.4 , 2.2	0.5, 1.9
2	0.1,8.8	0.4,6	0.7 , 4.6	0.7 , 4.6	0.9, 3.8	1,3.5	1.2, 3.2
5 ^a	1.2 , 13.2	2,10.2	2.7 , 8.5	2.7 , 8.4	3.2 , 7.4	3.4 , 7.1	3.7, 6.7
10	4 , 19.7	5.5 , 16.3	6.6 , 14.4	6.6 , 14.4	7.4 , 13.1	7.7 , 12.8	8.1, 12.2
20	11.3 , 31.5	13.6 , 27.7	15.2 , 25.5	15.3 , 25.4	16.4 , 24	16.8 , 23.5	17.4, 22.8
30	19.5 , 42.3	22.4 , 38.5	24.4 , 36.1	24.4 , 36	25.8 , 34.4	26.3 , 33.9	27.0, 33.2
42.7 ^b	30.8 , 55.3	34.2 , 51.5	36.5 , 49.1	36.5 , 49.0	38.1 , 47.4	38.6 , 46.9	39.4, 46.1
50	37.6 , 62.4	41.3 , 58.7	43.6 , 56.4	43.7 , 56.3	45.3 , 54.7	45.8 , 54.2	46.6, 53.4
70	57.7 , 80.5	61.5 , 77.6	63.9 , 75.6	64.0 , 75.6	65.6 , 74.2	66.1 , 73.7	66.8, 73.0
90	80.3 , 96	83.7 , 94.5	85.6 , 93.4	85.6 , 93.4	86.9 , 92.6	87.2 , 92.3	87.8, 91.9

a Of note, we expect to observe a lower percentage based on the findings of Wave 1. In Wave 1 of the study, a total of 61 patients had at least one LDL-C value available during the 6- month observation period (irrespective of baseline LDL-C data availability); among those, three patients (4.9%) had an LDL-C level of <25mg/dL.

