Twenty sites enrolled 68 patients in Wave 1 and 61 sites enrolled 251 patients in Wave 2. Although the remediation actions as outlined in Amended protocol 01 (21 December 2018) (Annex 3) are being taken during Wave 3 enrollment, the target total sample size of 875-890 will not be reached at the end of the recruitment period of the Wave 3. Based on the current projection, the total number of sites enrolled in Wave 3 is expected to be ranging from 36 to 63 due to both recruitment challenges and the impact of Coronavirus disease 2019 (COVID-19) at the time of sites selection, and these sites are expected to enroll 135 to 255 patients. However, best efforts will be made to enroll as many eligible patients as possible not limiting to 255 in Wave 3. The total number of patients enrolled in this study is expected to range from approximately 454 to 574.

09-Jul-2020 Version number: 1

Table 1 - Study size

	Patients planned in 2018	Sites planned in 2018	Actual/projected Patients	Actual/projected sites
Wave 1	75-90	25-30	68	20
Wave 2	400	90	251 ^a	61
Wave 3	400	90	135-255 ^b	36-63
Total	875-890	205-210	Approximately 454-574	Approximately 117-144

a 251 patients will be included in the Wave 2 interim report. Additional 25 patients may be available in the final study report once queries are resolved, which may bring the total patient number in Wave 2 to 276.

Data analysis:

Descriptive analyses will be conducted for each wave separately. In addition, analyses will be conducted using all the data obtained from all 3 waves. Point estimates of proportions and 95% confidence intervals will be calculated. For continuous outcome measures, means and standard deviations will be calculated.

The following descriptive analyses will be presented according to different parameters:

- Primary analyses:
 - Occurrence of very low LDL-C levels (both definitions of very low LDL-C <25 mg/dL [0.65 mmol/L] and <15 mg/dL [0.39 mmol/L] will be presented),
 - Evolution of LDL-C level after the occurrence of very low LDL-C level,
 - Change in treatment after the occurrence of very low LDL-C level.
- Secondary analyses:
 - The starting dose of Praluent,
 - The dosage regimen modification of Praluent,
 - Timing of LDL-C tests,
 - Discontinuation of Praluent: reasons will be described, if available,
 - Reason for Praluent prescription,
 - Adverse events.

Statistical tests will be performed at the 5% global significance level using 2-sided tests.

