9.7.1 Primary analysis

Descriptive analyses will be conducted for each wave separately. In addition, analyses will be conducted using the entire data of all 3 waves.

Point estimates of proportions and 95% confidence intervals will be calculated.

Data will be summarized using mean, first quartile, median, third quartile, standard deviation and range for continuous parameters and counts, percentages and 95% confidence intervals if needed for categorical parameters. The analyses will be performed, overall, by countries, and for specific analyses (starting dose of Praluent, occurrence of very low LDL-C level) will also be presented based on baseline LDL-C levels.

The following descriptive analyses will be presented on the eligible population:

A. Occurrence of very low LDL-C level

An LDL-C level <25 mg/dL (0.65 mmol/L) is defined as very low; and an alternative definition with a cut-off at 15 mg/dL (0.39 mmol/L) will also be used.

For each definition of very low LDL-C level, the following statistics will be calculated:

- 1. The proportion of patients who have at least 1 very low LDL-C level during the 6-month observational period:
 - (1) In the whole analysis population,
 - (2) According to baseline LDL-C level (<70; 70 to <100; 100 to <130; 130 to <160; 160 to <190; ≥190 mg/dL),
 - (3) According to Praluent starting dose.
- 2. All occurrences of very low LDL-C levels will be classified according to the Praluent regimen received at the time of the corresponding LDL-C test.

B. Evolution of LDL-C level after the occurrence of very low LDL-C level

- 1. Among the patients who have a LDL-C level of <25 mg/dL (0.65 mmol/L) at any dose, the proportions of patients whose LDL-C level returns to ≥25 mg/dL (0.65 mmol/L) within 8 weeks after the lab test, if data available, and at any time until the end of the 6-month observational period after index date, respectively.
 - (1) Overall,
 - (2) By the action of dosage regimen modification or discontinuation of Praluent, or change in dosing frequency of Praluent, or lowering doses of other lipid-lowering drugs, or discontinuation of other lipid-lowering drugs.
- 2. Same analysis will be conducted for the patients who have LDL-C level <15 mg/dL (0.39 mmol/L).

C. Change in treatment after the occurrence of very low LDL-C level

For each definition of very low LDL-C level, the following statistics will be calculated:

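### The 1.85 to 2.1 point half-width in Section 9.5.1 and Table 3 treats patients as independent although they are sampled within physicians, so it is a best case and should be restated with a design effect

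*Protocol*

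**What the plan says.** Section 9.5.1 introduces Table 3 with "The following table shows the exact 95% confidence intervals for a range of possible proportions of patients". For the pooled analysis it takes a "total number of patients ranging from approximately 454-574", "assuming approximately 5% of the patients will have an LDL-C level of <25 mg/dl based on the observed data for Wave 1", and states that "the half-width will range from 1.85% (95% CI = 3.4, 7.1) to 2.1% (95%CI=3.2, 7.4) for the observed proportion of 5" percent. It then calls this precision sufficient.

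Section 9.2.4.2 describes sampling within prescribers: "For each participating physician, up to 8 patients will be randomly enrolled". For two physicians of one practice in the same wave, "the combined total number of patients selected from these 2 physicians will be limited to 10". Table 1 in Section 4 puts the total number of sites at "Approximately 117-144".

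On the analysis, Section 9.7.1 says "Point estimates of proportions and 95% confidence intervals will be calculated" and names no interval method. Sections 9.5 and 9.7 mention no ICC, design effect or clustering by physician or practice.

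**The concern.** Patients who share a physician tend to resemble one another. The physician chooses the starting regimen, decides when LDL-C is tested and reacts to a low value. Section 9.7.3 itself plans to stratify by physician usage patterns because they may affect the results. With positive within-physician correlation, a sample of 454 patients from 117 sites carries less information than 454 independent patients, and an interval computed at the full patient count is too narrow.

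This matters because the pooled half-width is the protocol's stated numerical support for going on with 454 to 574 patients after the 875 to 890 planned in 2018 proved out of reach. The same issue touches the wave-by-wave estimates. A physician may take part in only one wave, so differences between physicians, of whom there are only 20 in Wave 1, enter the comparison across waves that Section 9.2.1 intends.

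**Working it through.** **Inputs from the protocol.** Pooled N of 454 to 574 and proportion 5% (Section 9.5.1). Sites: 20 + 61 + 36 = 117 to 20 + 61 + 63 = 144 (Table 1). Cap of 8 patients per physician (Section 9.2.4.2).

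**Assumptions, not in the protocol.** ICC 0.01 to 0.20. Coefficient of variation (CV) of cluster size 0 (equal clusters) to 0.6.

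**Step 1: reproduce the stated figure.** Clopper-Pearson limits with x = 0.05 × N and independent patients:

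- N = 454: 3.19% to 7.43%, half-width 2.12 (stated: 3.2 to 7.4, 2.1).
- N = 574: 3.37% to 7.11%, half-width 1.87 (stated: 3.4 to 7.1; the rounded limits give (7.1 − 3.4)/2 = 1.85).

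Other cells agree as well, for example at 5%: N = 68 gives 1.19 to 13.18 and N = 251 gives 2.65 to 8.47. The arithmetic is right, and it contains no allowance for clustering.

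**Step 2: mean cluster size.** m = 454/117 = 3.88 and 574/144 = 3.99. Wave 1 is 68/20 = 3.40 and Wave 2 is 251/61 = 4.11.

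**Step 3: design effect.** DEFF = 1 + [(1 + CV²) × m − 1] × ICC, and effective sample size = N/DEFF. Two examples at N = 454 and ICC 0.10:

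- CV 0: DEFF = 1 + 2.88 × 0.10 = 1.288, effective N = 352.5, interval 2.97% to 7.82%, half-width 2.43.
- CV 0.6: DEFF = 1 + (1.36 × 3.88 − 1) × 0.10 = 1.428, effective N = 318, half-width 2.56.

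**Step 4: half-width in points at 5%.** The first figure is for CV 0, the second for CV 0.6.

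| ICC | N = 454 | N = 574 |
|---|---|---|
| 0 (as in the protocol) | 2.12 | 1.87 |
| 0.01 | 2.15 to 2.17 | 1.90 to 1.92 |
| 0.05 | 2.28 to 2.35 | 2.02 to 2.08 |
| 0.10 | 2.43 to 2.56 | 2.15 to 2.27 |
| 0.20 | 2.70 to 2.95 | 2.40 to 2.62 |

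At ICC 0.05 to 0.10 the interval is about 7% to 21% wider (2.28/2.12 = 1.075; 2.56/2.12 = 1.21). For Wave 1 alone (N = 68, equal clusters) the half-width goes from 5.99 to 6.40 at ICC 0.05 and 6.78 at ICC 0.10.

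**Step 5: coverage, if the final intervals also ignore clustering.** Beta-binomial simulation with 117 sites, cluster sizes 1 to 8 with a mean just under 4, and a nominal 95% exact interval at the full patient count:

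| ICC | True proportion 5% | True proportion 50% (such as a starting dose) |
|---|---|---|
| 0.05 | about 94% | about 93% |
| 0.10 | about 92% | about 91% |
| 0.20 | about 88% | about 86% |

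At ICC 0.01 coverage at 5% stays at or slightly above 95%, because the exact interval is conservative.

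**The case against.** The strongest reply is that the effect is small and its size assumed. No ICC appears in the protocol; at 0.01 the half-width moves by about 0.03 points and coverage is nominal. The quoted figure concerns a laboratory value below 25 mg/dL, which may cluster less than prescribing choices do. The study is descriptive, the checklist in Annex 2 states that no hypothesis is tested, and no precision threshold is set. Section 9.5.2 accepted a half-width of 11.8% for Wave 1 at an earlier stage. Moving from 2.1 to between 2.3 and 2.6 points is unlikely to overturn the judgement of sufficiency. All of this stands. It limits the severity but does not make the stated figure more than a best case.

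A reader might infer that the reported intervals will certainly under-cover. The protocol does not support that: 9.7.1 names no interval method, Section 9.7 is presented as a specification for the SAP, and the SAP is not shown. The coverage figures are conditional on clustering being ignored there too.

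A reader might also infer that the cap of 8 leaves patients of high-volume prescribers under-represented and that the pooled estimate must be weighted. Section 9.7.3 partly meets this: it compares enrolled prescribers with the prescriber population by level of prescription, stratifies if they differ, and allows for statistical adjustment. The cap binds only where a site lists more than 8 candidates, against a mean of about 4 enrolled. Physicians are not a probability sample either (Section 9.2.4.1), so roster weights would correct only the within-physician stage.

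**Conclusion.** The point holds for the planning figures. Section 9.5.1 and Table 3 describe independent patients, the design samples patients within physicians, and the stated 1.85 to 2.1 points is the lower end of what the design may deliver. The direction is certain for any positive ICC. The size rests on the assumed ICC and cluster-size variation: negligible at ICC 0.01, 2.02 to 2.56 points at ICC 0.05 to 0.10 across both sample sizes, and up to 2.95 points at ICC 0.20. Nothing in the protocol shows that the study is too small or that a conclusion would change. This should be fixed, but it does not undermine the study.

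**What to change.** Restate the half-widths in Section 9.5.1 and Table 3 with a design effect over an assumed ICC range, for example 0.01 to 0.20, using the planned mean of about 4 patients per site and a stated cluster-size variation. Then say whether the precision is still judged sufficient. In Section 9.7.1, specify that 95% confidence intervals use physician or practice as the cluster: an exact interval on the effective sample size for rare proportions, and a robust variance otherwise. Weighting by roster size is at most an optional sensitivity analysis alongside Section 9.7.3, and would need roster size carried into the dataset.

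The cost is analysis code, revised text and slightly wider intervals. No additional patients or clinical data are needed.
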